Recruitment via social media. We will recruit participants through a targeted social media advertisement campaign. Recruitment through social media offers the advantage of being able to reach veterans outside the VA system and immediately deliver an online intervention.

We will use Facebook as our primary platform for recruitment; however, in consultation with our partners including the Oregon Health and Science University (OHSU) Strategic Communications social media team, we may include advertisements on other platforms for which they have extensive experience running campaigns (e.g., Instagram). Following a procedure developed in our previous research,³⁶ we will set ads to be presented to Facebook users likely to fit our eligibility criteria. Examples of characteristics we will use include: age, military-related interests or behaviors (e.g., making a charitable donation to a Veteran service organization, listing the military as their industry or employer), and “liking” Facebook pages related to Veterans, suicide prevention, or related topics. Ads will be placed in users’ “News Feeds” and optimized for computer and mobile devices. To assure that sensitive information is not sent in an unencrypted email, these ads will not invite communication from participants. From these feeds, participants will click on the ad and be taken to screening and consent in OHSU REDCap to enter the survey. Ad performance will be monitored in real-time, allowing the potential to retain only the most cost-effective ads in the campaign. The research team will collaborate closely with the OHSU Strategic Communications Social Media team to host ads, and monitor, audit and report on interval progress of the communication campaign. OHSU REDCap captures and stores the number of screened and consented participants and stores this information; we will be able to view and monitor recruitment progress by logging into REDCap and checking these numbers.

Based on our preliminary work recruiting Iraq/Afghanistan-era veterans, budget for recruitment, and empirical data on the slower pace of recruitment for web-based intervention studies that include close supports as participants,^{34, 49} we estimate a 10-week recruitment period to meet our target enrollment of 200 participants (20 participants/week).

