Qualitative Data Analysis: We will employ qualitative content analysis with a directed grounded theory approach.⁷¹ We have chosen this approach because it will allow us to identify tacit and implicit content in transcripts and use our conceptual framework and theory to guide our initial codebook.⁷² The investigative team (Drs. [name], [name], and [name]) will review the first transcript, discuss general impressions and insights, and develop a preliminary codebook. Full coding of the transcripts will then begin with each transcript being double coded by team members with at least two years’ experience analyzing qualitative data. We will use open coding to add relevant, unexpected, and emergent themes. Conceptual memos to track developing themes and parent/child nodes showing the interrelationship among codes will be created as necessary. Supervised by the investigative team, the coders will review areas of disagreement in coding, develop a consensus, and iteratively refine the codebook as needed. For data management we will use the software program Atlas.ti and use an audit trail to document creation and modification of codes.

Study Endpoints. The study will conclude with an assessment of feasibility and acceptability based on a mixed methods analysis of the quantitative (200 surveys, measures in **Table 2**) and qualitative data (15 interviews) collected. This will contribute towards the design of a larger RCT and may contribute to submission of journal articles for dissemination of findings.

Study Population

Eligibility Criteria. All potential participants will be identified through the targeted social media advertising campaign. After a potential participant clicks on an ad, they will complete a screening that will take place prior to consent. Half of the participants will be randomized to the intervention and half to the control condition. The eligibility criteria are presented in **Table 3** below. Through the targeted social media advertisement campaign, we will recruit recently transitioned veterans (active duty within past 12 months) who have at least weekly social contact with another veteran, and we will recruit friends or family of veterans who have at least weekly social contact with a veteran. Potential participants will be excluded for lacking necessary means of contact for follow-up, lacking fluency in English needed because the

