intervention is delivered in English, having already been exposed to the intervention, or misrepresenting their Veteran status.

Table 3: Eligibility Criteria

Inclusion Criteria	Exclusion Criteria
1a) Veteran who has served on active duty in the U.S. Armed Forces within the prior 12 months, or 1b) family member or friend of a Veteran	1) lack a U.S. phone number, email, or computer access 2) not fluent in English 3) have previously taken or intend to take PsychArmor S.A.V.E. training (to minimize contamination of the control group) 4) duplicate study entry or misrepresentation of Veteran status. ⁷³
2) social contact with a Veteran at least weekly	

Number of Participants. In order to obtain a final study sample of 200 participants (half randomized to the intervention and half to the control condition), we anticipate consenting and enrolling a higher number of participants as shown below:

Number of intervention group participants consented: 400

Number of participants enrolled (assumes 50% enroll): 200

Number of participants analyzed (assumes 50% lost to follow-up): 100

Number of control group participants consented: 400

Number of participants enrolled (assumes 50% enroll): 200

Number of participants analyzed (assumes 50% lost to follow-up): 100

Number of total participants consented: 800

Number of total participants enrolled (assumes 50% enroll): 400

Number of total participants analyzed (assumes 50% lost to follow-up): 200

Exclusion of Children. In addition to the above exclusion criteria, we will also exclude children under age 18 years. Children would not qualify as Veterans and would typically not be considered a close support to Veterans due to their young age. The primary focus of this study is looking at the outreach and uptake of online training in an adult population that can be difficult to reach through other means (for example, Veterans that don't use VHA services for their health care) and are at risk of depression and suicide. Although children can suffer from depression and suicide, the proposed methods of this study (an online platform) may not adequately address the sensitive nature of working with children under 18 that are at risk for suicide. Additionally, the military-focused gatekeeper training contained in this study has not been studied or tailored to a younger audience.

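### The plan uses 200 both as the number enrolled before loss to follow-up and as the number analysed after 50% loss from 400 enrolled

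*Combined protocol and SAP*

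**What the plan says.** Two accounts of the sample size stand in the same document.

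**200 enrolled, counted before loss.** Recruitment via social media (under Research Design and Methods) says "we estimate a 10-week recruitment period to meet our target enrollment of 200 participants (20 participants/week", and Subject Identification/Recruitment repeats it. The Timetable allots 2.5 months to recruitment, which matches ten weeks but gives no enrolment number. Sample Size Considerations obtains 200 as 56% of 357 eligible people, applies 42% loss to that same 200 for Hypothesis 1.3, and takes 100 as the treatment arm for Hypothesis 2.

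**200 analysed, counted after loss.** Number of Participants, under Study Population, treats 200 as the final sample and says "we anticipate consenting and enrolling a higher number of participants as shown below". The totals that follow are "Number of total participants consented: 800", then "Number of total participants enrolled (assumes 50% enroll): 400", then "Number of total participants analyzed (assumes 50% lost to follow-up): 200". The same steps are listed by arm, starting from "Number of intervention group participants consented: 400".

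Study Endpoints refers to a "mixed methods analysis of the quantitative (200 surveys, measures in" Table 2. It does not say whether these are baseline or six-month surveys, so it fits either account.

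**The concern.** Both accounts use the word enrolled, and they differ by a factor of two. The enrolment target fixes when recruitment stops, how long it takes, how many people have six-month data, and the n behind the sample size intervals. Feasibility is the trial's first aim, and Hypotheses 1.1 to 1.3 are about enrolment pace, enrolment proportion and loss, so these quantities need one definition before data arrive. The measurement characteristics intended for the larger trial are a named deliverable. At six months they rest on however many people remain.

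The denominators shift as well. Number of Participants applies its 50% enrolment rate to people who have consented. Hypothesis 1.2, the feasibility measures and Sample Size Considerations apply the rate to people who are eligible. Number of Participants also lists consented people by arm, although arm is assigned only after consent (Subject Identification/Recruitment; Step-by-Step Guidance, step 2.6).

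**Working it through.** **Inputs.** Target enrolment 200, 20 per week, 10 weeks (recruitment sections). 357 eligible, 56% enrolment, 42% loss, treatment-arm n = 100, mean 73%, SD 15%, 95% exact binomial and t intervals (Sample Size Considerations). 800 consented, 400 enrolled, 200 analysed, 50% at each step (Number of Participants).

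**Step 1: each section reproduces from its own inputs.**
- Recruitment: 20 × 10 = 200.
- Hypothesis 1.2: 200/357 = 56.0%; Clopper-Pearson 95% CI 50.7% to 61.2%, as stated.
- Hypothesis 1.3: 0.42 × 200 = 84; CI for 84/200 is 35.1% to 49.2%, as stated.
- Hypothesis 2: 73 ± t(0.975, 99) × 15/√100 = 73 ± 2.98, giving 70.02% to 75.98%, as stated.
- Number of Participants: 200/(1 − 0.5) = 400, and 400/0.5 = 800, as stated.

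So no section contains an arithmetic error. The conflict is over what 200 counts.

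**Step 2: suppose 200 enrol.** The number with six-month data is 200 × (1 − 0.42) = 116, or 200 × (1 − 0.50) = 100. Neither is the 200 analysed. To have 200 at six months with 42% loss would need 200/0.58 = 345 enrolled, or 345/20 = about 17 weeks.

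**Step 3: suppose 400 enrol.** Recruitment takes 400/20 = 20 weeks, or needs 400/10 = 40 per week to finish in ten. Eligible people needed: 400/0.56 = 714, not 357.

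**Step 4: the benchmarks at both sizes, using the plan's assumed rates.**

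| Hypothesis | 200 enrolled | 400 enrolled |
|---|---|---|
| 1.2: 56% enrol, lower limit above 50% | 200/357: 50.7% to 61.2% | 400/714: 52.3% to 59.7% |
| 1.3: 42% lost, upper limit below 50% | 84/200: 35.1% to 49.2% | 168/400: 37.1% to 47.0% |
| 2: mean 73%, SD 15%, lower limit above 70% | n = 100: 70.02% to 75.98% | n = 200: 70.91% to 75.09% |

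All pass at either size. If 400 is meant, the printed intervals are wider than they need be, so they err on the conservative side.

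**Step 5: the cut-off for Hypothesis 1.3 moves.** The largest loss whose exact upper limit stays below 50% is 85/200 = 42.5% (upper limit 49.67%; 86/200 gives 50.17%). At 400 it is 179/400 = 44.75% (49.77%; 180/400 gives 50.02%). An observed loss of 44% would therefore fail with 200 enrolled (88 lost) and pass with 400 (176 lost).

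**Step 6: precision at six months.** For a normally distributed measure with arms pooled (an assumption), the 95% CI for an SD is the observed SD times √((n − 1)/χ²), with χ² at its 97.5% and 2.5% points on n − 1 degrees of freedom. The multiples are 0.88 to 1.16 at n = 100, 0.89 to 1.15 at n = 116, and 0.91 to 1.11 at n = 200.

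**The case against.** The best counter-reading is that Number of Participants gives a ceiling for ethics approval, and that its remark about enrolling more people already explains the gap between enrolled and analysed. That remark does explain the section's own numbers. But the text calls them anticipated, not a maximum, and it mentions neither the 200 enrolment target, nor the ten weeks, nor the sample size calculation. Those sections never mention 400.

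A second objection is that little depends on the answer. None of the four hypotheses needs 200 people with six-month data: three are rates, and Hypothesis 2 is measured straight after training. Most measures are also collected earlier, and the plan allows multiple imputation or full maximum likelihood. This largely stands and limits the seriousness of the point. The loss of precision at six months is modest, and the normal-theory SD interval does not suit the count and yes/no measures. What remains is a wrong stated size and a decision cut-off that depends on n.

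Third, 20 per week is a benchmark, not a cap, and the team's earlier campaign reached about 100 per week. That campaign was for a cross-sectional study, however. The present plan bases its slower pace on, among other things, "budget for recruitment, and empirical data on the slower pace of recruitment for web-based intervention studies".

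Finally, the documents do not prove that 200 enrolled is the intended figure. That is so, and the sponsor must confirm it.

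**Conclusion.** The inconsistency is real and should be fixed. Planned enrolment is 200 in the recruitment sections and the sample size section, and 400 in Number of Participants. The shortfall in six-month data is 84 people (200 − 116) at 42% loss or 100 at 50% loss if 200 enrol. If 400 enrol, recruitment runs ten weeks over at the stated pace. At the plan's assumed rates (56% enrolment, 42% loss, mean completion 73% with SD 15%) no benchmark changes from pass to fail. A decision would differ only if observed loss fell between the two cut-offs, above 42.5% and up to 44.75%. The finding on size rests only on the plan's own figures; the SD multiples also need the normality assumption.

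**What to change.** **Main fix: keep 200 enrolled.** Both recruitment sections and Sample Size Considerations already use it, and the 2.5-month timetable is consistent with it.
- Restate Number of Participants as about 357 eligible; 200 enrolled and randomised, 100 per arm; about 116 with six-month data at 42% loss, or 100 if 50% is kept as a stated worst case.
- Give the number consented as one total, not by arm, and label it an assumption, because the plan gives no rate for loss between consent and randomisation.
- Define eligible, consented and enrolled once (for example, enrolled means consented and randomised at step 2.6). Use eligible people as the denominator for Hypothesis 1.2 and all enrolled for Hypothesis 1.3.
- In Study Endpoints, say whether the 200 surveys are baseline or six-month surveys.

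This costs only wording, plus acceptance of a less favourable expected number at six months.

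**Alternative, only if the sponsor does intend 400 enrolled.** Leave the 400 and restate both recruitment sections, the Timetable and Sample Size Considerations: about 714 eligible at 56%, 200 per arm, 20 weeks at 20 per week. This adds about ten weeks of recruitment, draws further on the recruitment budget, and doubles survey payments to completers (400 × 0.58 = 232 against 116). The payment wording allows more than one reading. At $20 once plus $20 at the end, the totals are 232 × $40 = $9,280 against 116 × $40 = $4,640. At $20 for each of six monthly surveys plus $20 at the end ($140), they are $32,480 against $16,240. Payments for the 15 interviews do not change.

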The study will take place at the VA Portland Health Care System (VAPORHCS) in Portland, Oregon. OHSU will be the coordinating center for the study. The VAPORHCS HSR&D Center of Innovation is the Center to Improve Veteran Involvement in Care (CIVIC) is where the science of this research study will take place, in collaboration with other CIVIC investigators, staff, and the CIVIC Veteran Engagement Group.

Most project personnel will be located at the Center to Improve Veteran Involvement in Care (CIVIC). CIVIC will provide office space, equipment, and administrative research support to project staff. [name] and his research staff retain private office space in CIVIC. CIVIC has approximately 4,500 square feet of office space, which includes the second and third floors of VAPORHCS Building 6. This contiguous space allows extraordinary opportunities for collaboration and synergy. All necessary equipment including computers, printers, copiers, and scanners are available to the research team. [name] will devote 2/8 time to this study, and his study coordinator will be devoting 8/8 time to this study.

Subject Compensation/Payment:

Participants will receive compensation because they are taking time out of their day to complete the surveys, intervention training, and interviews. All participants who complete their follow-up surveys will receive compensation valued at \$20 and an additional \$20 at the completion of the study. The subset of 15 participants who complete an interview will also receive compensation valued at \$25 as a thank you for their time. Participants may be paid according to their preferences via cash (in the case of any local participants of interviews who may choose to come in), Electronic Funds Transfer, mailed check, ClinCard, gift card, or other allowable VA payment method suitable for paying participants remotely. These compensation terms are included in the information sheet provided during consent. Additional identifiers may be collected for payment purposes; depending on payment method, identifiers may be stored in REDCap, VA server only accessible to the study team, or on a secure payment site (such as ClinCard).

The compensation offered is a fair amount for the time and effort involved for each section of study participation. It is enough to encourage completion and is not so large as to constitute undue pressure or influence. Compensation will not be prorated for participants who do not complete the study because the cost is low and our sample large, thus making prorated payments difficult to manage for a pilot project.

Privacy and Confidentiality:

Privacy and confidentiality will be maintained in accordance with HIPAA regulations. Numerous efforts will be made to minimize the likelihood of the risk of a breach of confidentiality. The project manager will conduct a review of study files every six months to assure compliance with approved procedures. The research team will work closely with the VAPORHCS Information Security Officer and Privacy Officer to ensure that any data transfer, storage, and handling by non-VA entities adhere to VA security policies.

The confidentiality of participants will be protected in the following ways:

- Unique identifiers will be assigned to all participants at the time of electronic consent and kept consistent for the duration of the study.
- Surveys, administrative data, and all other measures related to individual participants will contain the ID number instead of names or other PHI.
- A master list linking names and ID numbers will be stored in a password-protected electronic file, located behind the VA firewall on a secure server or in locked file cabinets, separate from other study data and accessible only to IRB-approved research personnel.
- With the exception of zip codes needed to assess rurality, all identifiable information will be removed from datasets prior to statistical analyses. We will analyze and report participant data in aggregate form only, and no PHI will be reported for any participant.
- Access to study data will be limited to IRB-approved study personnel and those with regulatory oversight responsibilities, and all study staff will complete the required research ethics, data security, and HIPAA training within the prior 12 months.
- Any hard copies of data will be stored in locked file cabinets in locked rooms.
- No study data will be stored on laptops unless they meet data security policies.
- The study data will be managed and stored in OHSU's instance of REDCap, a highly secure and robust web-based research and data collection and management system, and in a password and firewall protected network drive on the secure (Veterans Health Administration) VHA network accessible only to study staff.
- Access to the REDCap database will be limited to IRB-approved study staff. See Protection of Risk subsection of Risk and Side Effects section for a description of REDCap's security features.

With the exception of ZIP Codes needed to assess rurality, all other identifiers will be removed from the dataset prior to export from REDCap. Data containing the ZIP Code identifiers may be stored on OHSU Box, an institution supported, cloud-based file sharing and storage option with added protections in place for OHSU confidential and restricted data or protected health information. Box.com adheres to the highest industry standards for security and is compliant with HIPAA requirements as well as federal government agency requirements such as the Department of Defense. All files uploaded to Box are encrypted at rest using 256-bit AES encryption, and further protected by an encryption key-wrapping strategy. The company also offers customer-managed encryption keys. Box provides you with in-depth, unchangeable audit logs, user permission options and restrictions, and organization-wide controls and permissions. OHSU and Box have entered into a Business Associate Agreement, including a data use agreement, that meets all OHSU privacy, confidentiality, and information technology policy compliance requirements. This includes requirements for software applications to use specific login IDs, passwords, OHSU-approved encryption, audit software, and reporting requirements to privacy officers when becoming aware of any users not in compliance. Only study personnel with VAPORHCS appointments will work with identifiable data.

Any transfer of data containing identifiable information between the VA network and Box.com will utilize encrypted email or encrypted flash drives.

For communication with participants, we will take special precautions to preserve privacy, confidentiality, and data security. Personal email accounts will not be used for research communications with participants. These communications will not contain PII/PHI. Any email communication that does contain PII/PHI will be encrypted and sent via Azure Rights Management Services (RMS).

For the qualitative interviews, individual interviews will be digitally audio-recorded using a handheld VA audio recorder. After the interviews, digital recordings will be uploaded on a password secured server behind the VA firewall. Recordings will then be deleted from the audio recorder. Audio recordings will not be destroyed since they will contain the verbal consent for the recorded interviews. Filenames of digital recordings will not include participant names; only a unique study ID number will be listed in filenames.

Transcriptions will be de-identified during the transcription process by personnel who have training and experience in transcription. Audio recordings may be sent to the VHA Salt Lake City (VHASLC) Centralized Transcription Services Program (CTSP) for transcription services. Only study personnel will have access to de-identified transcripts. Any hardcopies made of transcripts will be kept in locked files in investigators' offices. We will ensure that any quotations used in manuscripts or reports do not contain identifying information. Upon completion of the study, all audio files and documents containing participants' names and other identifying information will be destroyed.

Certificate of Confidentiality

N/A. The study does not include a Certificate of Confidentiality.

Information and/or Specimen Management

Unique identifiers will be assigned to all participants at the time of electronic consent and kept consistent for the duration of the study. Surveys, administrative data, and all other measures related to individual participants will contain the ID number instead of names or other PHI. A master list linking names and ID numbers will be stored in a password-protected electronic file, located behind the VA firewall on a secure server or in locked file cabinets, separate from other study data and accessible only to IRB-approved research personnel.

Survey data will be captured and stored in REDCap, which employs a robust multi-level security system that enables researchers to easily implement "minimum necessary" data access for their research staff, including specification of data fields that are identifiers. This feature includes a "single click" ability to provide completely deidentified (removing all identified data fields and shifting dates) for analysis or other purposes. All HIPAA identifiers contained in our dataset except for ZIP Code, used to assess rurality, will be removed prior to data analysis. Other identifiable information that was collected, such as names and email addresses will only be accessed, separate from any health data, to send out invitations and reminders for follow-up surveys and interviews.

For the qualitative interviews, individual interviews will be digitally audio-recorded using a handheld VA audio recorder. After the interviews, digital recordings will be uploaded on a password secured server behind the VA firewall. Recordings will then be deleted from the audio recorder. Audio recordings will not be destroyed since they will contain the verbal consent for the recorded interviews. Filenames of digital recordings will not include participant names; only a unique study ID number will be listed in filenames. Transcriptions will be de-identified during the transcription process by personnel who have training and experience in transcription. Audio recordings may be sent to the VHA Salt Lake City (VHASLC) Centralized Transcription Services Program (CTSP) for transcription services. Only study personnel will have access to de-identified transcripts. Any hardcopies made of transcripts will be kept in locked files in investigators' offices. We will ensure that any quotations used in manuscripts or reports do not contain identifying information. Upon completion of the study, all audio files and documents containing participants' names and other identifying information will be destroyed.

All information linking study data to PHI will be kept within VAPORHCS electronically in secure computer files stored behind firewalls requiring password access, or in hardcopy form in locked file cabinets in locked offices. Except for ZIP Codes, all patient identifiers will be removed prior to analysis. All investigators and team members who will have access to the data will have received appropriate background checks as part of hiring and/or credentialing, and will have completed Data Security Training within the prior 12 months.

Disclosure/Sharing:

N/A. The study does not include disclosure/sharing outside the IRB-approved VAPORHCS study personnel.

Transfer of Data Ownership

OHSU will have ownership of research data for this research study.

Web Application(s), Mobile Device(s) and/or Mobile Application(s):

Facebook ads will be used for study recruitment. On Facebook advertising, all consumer data is automatically "hashed," meaning their unique identifiers are stripped before we (the advertisers) gain access to the information. The only info we see is basic demographics, geographic info and performance data.

After interested individuals click on an ad, they will be brought to a study website landing page. This website will be hosted and managed through OHSU's instance of REDCap,⁷⁴ a highly secure, web-based application that allows study participants to access materials from any computer and stores data on a server at OHSU, separate, secure and independent of Facebook. Eligibility questions, consent, questionnaires, and presentation of intervention will all be done through REDCap.

REDCap employs a robust multi-level security system that enables researchers to easily implement "minimum necessary" data access for their research staff, including specification of data fields that are identifiers. User activities are logged to enable auditing of all data access. Access is integrated with OHSU's network such that users who are also OHSU employees are authenticated against their OHSU network credentials.

For communication with participants, we will take special precautions to preserve privacy, confidentiality, and data security. Personal email accounts will not be used for research communications with participants. VA email, email generated through OHSU REDCap, and SMS text messages sent through REDCap may be used to provide reminders about survey completion or related general communication about the study. REDCap uses a third party web service, Twilio Inc., to send automated SMS text messages. No PII/PHI besides the participant's phone number will be shared with Twilio and participants will be informed in the information sheet that their phone number may be shared with Twilio for this purpose. These communications will not contain PII/PHI. Any email communication that does contain PII/PHI will be encrypted and sent via Azure Rights Management Services (RMS).

Some data containing PHI may be stored on OHSU Box, an institution supported, cloud-based file sharing and storage option with added protections in place for OHSU confidential and restricted data or protected health information. Box.com adheres to the highest industry standards for security and is compliant with HIPAA requirements as well as federal government agency requirements such as the Department of Defense. All files uploaded to Box are encrypted at rest using 256-bit AES encryption, and further protected by an encryption key-wrapping strategy. The company also offers customer-managed encryption keys. Box provides you with in-depth, unchangeable audit logs, user permission options and restrictions, and organization-wide controls and permissions. OHSU and Box have entered into a Business Associate Agreement, including a data use agreement, that meets all OHSU privacy, confidentiality, and information technology policy compliance requirements. This includes requirements for software applications to use

specific login IDs, passwords, OHSU-approved encryption, audit software, and reporting requirements to privacy officers when becoming aware of any users not in compliance.

For the qualitative interviews with the subset of 15 participants, research staff will set up a time to speak with the participant over an agreed upon and VA-approved remote video modality (i.e. VA Video Connect, although in specified circumstances other video conferencing applications such as Apple Facetime, Facebook Messenger, Skype, Zoom, Cisco WebEx, or Google Hangouts may be used. Public facing applications will not be used). Participants will be informed that certain third-party video applications may introduce additional privacy risks. Research staff will use all available encryption and privacy modes.

Data and Safety Monitoring Plan (DSMP)

This study does not involve pharmaceuticals or medical devices. Data collection relies on self-report online surveys and interviews; no invasive testing or procedures are involved, and the intervention involves no direct contact with participants. The risks related to participation are likely much lower than those of a trial involving pharmaceuticals, medical devices, or somatic interventions or procedures. Nonetheless, we will very carefully monitor the progress of the study and any potential risks or adverse events.

Because the primary risk is a breach in confidentiality, no statistical analysis of safety data is planned. The study coordinator will monitor for breaches in confidentiality and problems will be addressed and reported according to regulations. Other safety information collected will include self-report information participants may tell us while filling out online surveys or, for a subset of 15 participants, through interviews. This data will be collected at the time of participation when participants enroll in the study and once a month for six months of follow-up surveys. The interviews will occur approximately one month post-intervention. PI [name] holds weekly meetings with his study personnel where they will discuss adverse events and protocol deviations associated with this project and ways to reduce repeat occurrences. Research staff will examine all cumulative adverse events quarterly to determine if there are any systematic problems and to implement protocol corrections as needed after receiving IRB approval.

Monitoring for any potential adverse events and protocol deviations will be performed by research staff that oversees data collection activities, including the interviewers or anyone else who has contact with study participants during study activities. [name] will be responsible for ensuring the absence of conflicts of interest within the research staff and training them in the responsible conduct of research and reporting adverse events. Any adverse event will be reported immediately to PI [name], who will contact the participant and determine if additional intervention is needed to ensure participant safety. Protocol deviations will also be immediately reported to [name] who will ensure that adverse events deemed to be unanticipated problems and protocol deviations are properly reported to the IRB in a timely manner. Detailed written documentation will be kept for all adverse events that occur over the course of the study. The balance of risk to benefit will be continuously monitored by the PI, and the study may be modified or terminated if risks begin to outweigh benefits.

Our data and safety monitoring plan includes adverse event (AE) and serious adverse event (SAE) monitoring by all staff working on the project. AEs will be identified by spontaneous reports to any study staff member, and all staff will be trained to be receptive to participant complaints and concerns about the study. Any breach of confidentiality will be considered an AE.

We will classify an AE as:

0 - No AE

- 1 - Mild - no treatment needed
- 2 - Moderate - resolved with treatment
- 3 - Severe - inability to carry on normal activities, required professional medical attention
- 4 - Life-threatening or disabling
- 5 - Fatal

The PI will review all adverse events to determine if they meet the definition of an Unanticipated Problem (UP). All Unanticipated Problems, including AEs that meet the definition of a UP as determined by [name], including breaches of confidentiality and participant complaints, will be reported to the IRB as soon as possible and within the following time frames:

- Deaths and potentially life-threatening events within 7 days of the PI learning of the event days.
- All other unanticipated problems will be reported within 15 days of the PI learning of the event.

If any AEs or UPs require a change to the protocol or consent form (as determined by the PI or IRB) the PI will submit the revised protocol for review and approval by the Joint IRB promptly. A brief summary of UPs and all adverse events will be submitted to the IRB at the time of annual continuing review. Adverse events, enrollment, and data collection problems will be reviewed quarterly by the PI. In addition, dropouts and AEs will be reviewed for patterns indicating problems with the study procedures. Any protocol deviation identified during the quarterly reviews will be reported per IRB policy.

Step-by-Step Guidance on Conducting the Study

1. Project Setup
 - 1.1. Social media campaign (**Appendix E**) development
 - 1.1.1. [name] to deliver workshop to develop messages for ad campaign
 - 1.1.2. Consultation with OHSU Strategic Communications social media team and a Veteran engagement representative
 - 1.1.3. Submit finalized social media ads to IRB for approval
 - 1.2. REDCap setup
 - 1.2.1. Build survey (**Appendix B**) in REDCap with consultation from Oregon Clinical and Translational Research Institute (OCTRI)
 - 1.2.2. Submit any substantive changes to survey to IRB for approval (if applicable)
2. Recruitment
 - 2.1. Implement social media ad campaign on Facebook
 - 2.1.1. Monitor recruitment pacing through REDCap
 - 2.2. Interested participants click on a link to connect to the study website on OHSU's REDCap
 - 2.3. Interested participants complete electronic eligibility screening
 - 2.4. Eligible participants will be directed to an information sheet (**Appendix A**) for electronic informed consent
 - 2.5. Consented participants provide contact information (name, phone number, email address) needed for follow-up (if participants choose to withdraw, they will be given the option to stop receiving communications of any format from the study team).
 - 2.6. Participants will be randomly assigned to either the intervention or control group trainings
3. Intervention
 - 3.1. Participants will complete the baseline survey (see table 2, reproduced below, for included measures)
 - 3.2. Participants will view either intervention gatekeeper training or control "sham" training
 - 3.2.1. Data collected on training completion rates

- 3.3. Participants will immediately complete a follow-up survey (see table 2 for included measures)
- 4. Longitudinal survey follow-up
